4.2 Pharmacokinetic Analysis

4.2.1 Plasma Concentrations

Analysis Set: Analysis	Pharmacokinetic Analysis Set		
Variable(s) :	Plasma concentrations of TAK-385 (ng/mL)		
Visit :	WK1D1 and WK5D1: Before dosing and 2 hours after dosing.		
	WK1D2, WK1D4, WK2D1, WK3D1, WK9D1, WK13D1, WK17D1,		
	WK21D1, WK25D1, WK37D1 and WK49D1: Before dosing		
Analytical			
Method(s) :	Descriptive statistics, geometric mean, and CV will be used to summarize		
	plasma concentrations at each visit for each treatment group.		
	Case plots as well as the mean and standard deviation plots of changes over		
	time will be provided for plasma concentrations for each treatment group.		

4.3.2 Serum Concentrations of LH, FSH, DHT, and SHBG

Analysis Set: Full Analysis Set

Analysis

Variable(s) :	(1) Serum Concentrations of LH (mIU/mL)
	(2) Serum Concentrations of FSH (mIU/mL)
	(3) Serum Concentrations of DHT (ng/mL)
	(4) Serum Concentrations of SHBG (nmol/L)
Visit :	Baseline, WK1D2, WK1D4, WK2D1, WK3D1, WK5D1, WK9D1,
	WK13D1, WK17D1, WK21D1, WK25D1, WK37D1, WK49D1, WK61D1,

WK73D1, WK85D1, WK97D1

Analytical

Method(s) :

The following analysis will be performed using the full analysis set. For the analysis variables (1) to (4), descriptive statistics of the observed values and the two-sided 95% confidence intervals of the mean will be provided for each visit by treatment group. The same analysis will be performed for the percent change from baseline. Case plots as well as the mean and standard deviation plots of changes over time will be provided for observed values for each treatment group.

4.4 Statistical/Analytical Issues

4.4.1 Adjustments for Covariates

Not applicable in this study.

4.4.2 Handling of Dropouts or Missing Data

Missing test results and data determined to be non-evaluable according to the Handling Rules for Analysis Data will not be used for hypothesis testing and estimations.

Values less than or equal to the lower limit of quantification will be treated as the value of the lower limit of quantification for PSA, serum testosterone, high-sensitivity serum testosterone, LH, FSH, DHT, and SHBG, and all others will be treated as zero when calculating the descriptive statistics.

Values less than the lower limit of quantification will be treated as zero for the calculation of descriptive statistics except for geometric mean for plasma concentration of TAK-385. For the geometric mean, values less than the lower limit of quantification will be treated as missing.

4.4.3 Interim Analyses and Data Monitoring

No interim analysis is planned in this study.

4.4.4 Multicenter Studies

Although this study is a multicenter study, treatment-by-center interaction will not be explored since the number of subjects for each center is not sufficient for such exploration.

4.4.5 Multiple Comparison/Multiplicity

Not applicable in this study.

4.4.6 Use of an "Efficacy Subset" of Subjects

Not applicable in this study.

4.4.7 Active-Control Studies Intended to Show Equivalence or Non-Inferiority

Not applicable in this study.

4.4.8 Examination of Subgroups

Not applicable in this study.

5 Safety Analysis (Part A)

In this study, safety will be evaluated as the primary endpoint.

5.1 Treatment-Emergent Adverse Events

Analysis will be performed on TEAEs that occurred in Part A.

5.1.1 Overview of Treatment-Emergent Adverse Events

Analysis Set:	Safety Analysis Set		
Analysis			
Variable(s) :	TEAE		
Categories:	Relationship to Study Drug Intensity		[Related, Not Related]
			[Grade 1, Grade 2, Grade 3, Grade 4, Grade 5]
Analytical			
Method(s):	The following summaries wi		l be provided for each treatment group.
	TEAEs wi	ll be graded using t	he National Cancer Institute-Common
	Terminolo	gy Criteria for Adv	verse Events (CTCAE) Version 4.03.
	(1) Ove	erview of Treatment	t-Emergent Adverse Events
	1)	All Treatment-Em	nergent Adverse Events (number of events,
		number and perce	ntage of subjects)
	2)	Relationship of Tr	reatment-Emergent Adverse Events to study
		drug (number of e	events, number and percentage of subjects)
	3)	Intensity of Treat	nent-Emergent Adverse Events (number of
		events, number an	d percentage of subjects)
	 4) Treatment-Emergent Adverse Events leading to study drug discontinuation (number of events, number and percentage of subjects) 5) Serious Treatment-Emergent Adverse Events (number of events) 		ent Adverse Events leading to study drug
			umber of events, number and percentage of
			t-Emergent Adverse Events (number of events,
number and percentage of subjects)		ntage of subjects)	
	6)	Relationship of se	rious Treatment-Emergent Adverse Events to
		study drug (numb	er of events, number and percentage of subjects)
	7)	Serious Treatmen	t-Emergent Adverse Events leading to study
		drug discontinuati	on (number of events, number and percentage of
subjects)		subjects)	
	8)	Treatment-Emerg	ent Adverse Events resulting in death (number
		of events, number	and percentage of subjects)
	 TEAEs will be counted according to the rules below. Number of subjects Summaries for 2) and 6) A subject with occurrences of TEAE in both categories (i.e., Related and 		ding to the rules below.

Not Related) will be counted once in the Related category.

• Summary for 3)

A subject with multiple occurrences of TEAE will be counted once for the TEAE with the maximum intensity.

• Summaries other than 2), 3), and 6)

A subject with multiple occurrences of TEAE will be counted only once. Number of events

For each summary, the total number of events will be calculated.

5.1.2 Displays of Treatment-Emergent Adverse Events

Analysis Set:	Safety Analysis Set	
Analysis		
Variable(s) :	TEAE	
Categories:	Intensity	[Grade 1, Grade 2, Grade 3, Grade 4, Grade 5]
	Time of Onset (day)	[1<=-<=7, 8<=-<=14, 15<=-<=21,
		22<= - <=Max]

Analytical

Method(s) :	The following summaries will be provided using frequency distribution for
	each treatment group.

TEAEs will be coded using the MedDRA and will be summarized using SOC and PT. SOC will be sorted alphabetically and PT will be sorted in decreasing frequency for tables provided by SOC and PT. SOC and PT will be sorted in decreasing frequency for tables provided by System Organ Class only or PT only.

TEAEs will be graded using the National Cancer Institute-Common Terminology Criteria for Adverse Events (CTCAE) Version 4.03.

- Treatment-Emergent Adverse Events by System Organ Class and Preferred Term
- (2) Treatment-Emergent Adverse Events by System Organ Class
- (3) Treatment-Emergent Adverse Events by Preferred Term
- (4) Drug-Related Treatment-Emergent Adverse Events by System Organ Class and Preferred Term
- (5) Drug-Related Treatment-Emergent Adverse Events by Preferred Term
- (6) Intensity of Treatment-Emergent Adverse Events by System Organ Class and Preferred Term
- (7) Intensity of Drug-Related Treatment-Emergent Adverse Events by

System Organ Class and Preferred Term

- (8) Treatment-Emergent Adverse Events with Intensity of Grade 3 or Higher by System Organ Class and Preferred Term
- (9) Treatment-Emergent Adverse Events Leading to Study Drug Discontinuation by System Organ Class and Preferred Term
- (10) Serious Treatment-Emergent Adverse Events by System Organ Class and Preferred Term
- (11) Treatment-Emergent Adverse Events by System Organ Class and Preferred Term Over Time
- (12) Special Interest Treatment-Emergent Adverse Events by System Organ Class and Preferred Term

The frequency distribution will be provided according to the rules below. Number of subjects

- Summary tables other than (6), (7), (8), and (11)
 A subject with multiple occurrences of TEAE within a SOC will be counted only once in that SOC. A subject with multiple occurrences of TEAE within a PT will be counted only once in that PT. Percentages will be based on the number of subjects in the safety analysis set.
- Summary tables for (6), (7), and (8)

A subject with multiple occurrences of TEAE within a SOC or a PT will be counted only once for the TEAE with the maximum intensity. Percentages will be based on the number of subjects in the safety analysis set.

• Summary table for (11)

A subject with a TEAE that occurs in more than one interval is counted in all the intervals that the TEAE occurs. For each time interval, a subject with multiple occurrences of TEAE within a SOC or a PT will be counted only once in that SOC or PT.

When calculating percentages for each time interval, the number of subjects at risk (i.e., subjects who either have an exposure or have an occurrence of TEAE, during or after the corresponding time interval) will be used as the denominator. The number of subjects whose onset of any one of the TEAEs is within the time interval will be used as the numerator.

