## 6.0 STUDY DESIGN AND DESCRIPTION

### 6.1 Study Design

This is a multicenter phase 1, open-label, dose range-finding study to evaluate the tolerability, safety, PK, and pharmacodynamics of TAK-385 alone in hormone treatment-naive Japanese patients with non-metastatic prostate cancer.

This study consists of two parts: Part A, a dose-rising phase, and Part B, an expansion phase. The designs of Part A and Part B are shown in “Study Design and Treatment Schema” (Figure 6.a and Figure 6.b).

In Part A, three to six patients will be enrolled in each cohort. Whether or not the study will proceed to the next cohort or Part B will be determined through assessment of tolerability at the dose in question, based on the incidence of DLT in the evaluation period (treatment initiation to Day 28).

TAK-385 will be taken once a day for 28 days at the doses assigned to each cohort. Cohort 1 will receive a loading dose of 320 mg and a maintenance dose of 80 mg, Cohort 2 will receive a loading dose of 320 mg and a maintenance dose of 120 mg, Cohort 3 will receive a loading dose of 320 mg and a maintenance dose of 160 mg, and Cohort 4 will receive a loading dose of 360 mg and a maintenance dose of 120 mg. The doses will be taken orally at least 30 minutes before breakfast. Patients being switched to a GnRH agonist (eg, leuprorelin) or a GnRH antagonist (eg, degarelix) following the completion of TAK-385 treatment in Part A will first pass through a 1-week observation (no-treatment) period. However, patients whose treatments were discontinued because they met the discontinuation criteria (Section 7.5) during the 28-day treatment period will not have to pass through this observation period.

If tolerability is confirmed in Cohort 2, then the study will proceed to Cohort 3 and Part B simultaneously. The tolerability in Japanese of the maximum dose at which tolerability was found in 28-day multiple dosing in the overseas phase 1 single-/multiple-dose study (TAK-385\_C27001) (160 mg) will be evaluated for the purpose of checking the tolerability of dose escalation to 160 mg in Part B as well as the PK. In the overseas phase 1 single-/multiple-dose study (TAK-385\_C27001), no findings indicative of safety problems were obtained in multiple dosing for 28 days with 160 mg. However, if tolerability is not confirmed in Cohort 2, then a cohort will be added that will receive a loading dose of TAK-385 320 mg and a maintenance dose of 40 mg.

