**Table 6.a Study Schedule (Part A)**

Screening		Treatment Period		Post-treatment Observation Period	Safety Follow-up
		DLT Evaluation Period (treatment initiation to Day 28)			
Outpatient	Inpatient	Outpatient	Outpatient/Inpatient	Outpatient	
Day -28 to Day -1*1	Day 1*1 to Day 15	Day 16 to Day 28*2	Day 29 to Day 35*2	...	30 to 40 days after the last dose of TAK-385
Screening tests Assessment of eligibility	Admission Treatment initiation Tests/observations	Discharge	Treatment completion Tests/observations	Initiation of other treatment Observations	Tests/observations

\*1: Day -1 and Day 1 are the day before treatment initiation and the day of treatment initiation, respectively.

\*2: Days 27 to 35 are performed either on an outpatient or an inpatient basis.

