### **9.3.8 Safety Follow-up**

The following tests, observations, and assessments will be performed as safety follow-up 30 to 40 days after the day of the last dose of study drug, and will be the final observations performed.

These same tests, observations, and assessments will be performed 30 to 40 days after the last dose of study drug for subjects who withdraw from the study as well.

The status of study completion will be entered into the eCRF for all subjects who receive study drug in Part A, and for all subjects who are randomized in Part B.

- Physical examination
- Vital signs
- Weight
- ECOG performance status
- 12-lead ECG
- Clinical laboratory tests (hematology, chemistry, metabolic panel, and urinalysis)
- Concomitant medications
- Concomitant therapies
- AEs

The following tests will be performed only in Part B.

- QOL assessments

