## 10.2 Procedures

### 10.2.1 Collection and Reporting of Adverse Events

#### 10.2.1.1 Collection Period of Pretreatment Events and Adverse Events

Pretreatment events will be recorded continuously from when informed consent is obtained until the first dose of study drug (Day 1). If it is decided that a subject should be withdrawn before the first dose of study drug, PTEs will be recorded until that point in time.

AEs will be recorded continuously from the start of study drug administration to subjects (Day 1) until the safety follow-up.

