**Appendix A Schedule of Study Procedures (Part A)**

Procedure a	Subject consent b	Screening	Treatment Period c										Post-treatment Observation Period d				Withdrawal e	SFU  30 to 40 days after the last dose
			Inpatient f					Outpatient										
			D1 h	D2	D3	D7	D12	D13	D14	D15	D21	D28	D29	D30	D31	D35 i		
Allowable visit window		Before treatment initiation D -28 to D -1 g	0					± 1	0	0	+ 3	+ 3	0	+ 7				
Confirmation of eligibility		X																
Subject background d		X																
Physical examination		X	X	X	X			X		X	X	X	X	X	X			
Vital signs k		X	X		X			X		X	X				X			
Weight/height l		X	X		X			X		X	X				X			
ECOG performance status		X								X					X			
12-lead ECG m		X	X o					X		X					X			
Chest X-ray examination		X																
Imaging assessment n		X	Measure as appropriate															
Hematology tests		X	X o		X			X		X	X				X			
Blood biochemistry tests		X	X o		X			X		X	X				X			
Blood lipid, sugar, etc. tests		X	X o							X					X			
Urinalysis		X	X o		X			X		X	X				X			
Heart-related tests		X	Measure as appropriate															
Pharmacodynamic assessments		X		X	X	X			X		X	X		X	X			
Tumor marker		X								X					X			
Pharmacokinetic assessments p			X	X	X	X	X	X	X	X	X	X	X	X	X q			
PGx sample collection			X (during the treatment period)															
Concomitant medications/therapies			Collected from the time of informed consent until 30 to 40 days after the last dose															
Adverse events, etc.		PTEs r	Information collected from study treatment initiation until 30 to 40 days after the last dose															
Study treatment			Oral doses once a day at least 30 minutes before breakfast															

Abbreviations: D = Day; ECOG = Eastern Cooperative Oncology Group; PGx = pharmacogenomics; SFU = safety follow-up

- 
- a Unless otherwise specified, the assessments will be completed before study drug dosing.
  - b Except for procedures that are normally part of a physical examination, subjects must sign the informed consent form before any study-related procedures are performed.
  - c Additional examinations/assessments may be performed at the discretion of the investigator or sub-investigator.
  - d Days 27 to 35 are performed either on an outpatient or an inpatient basis.

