5.3.2 Vital Signs, Physical Findings, and Other Observations Related to Safety	
5.4 Displays of Treatment-Emergent Adverse Events (Japanese)	
6 Safety Analysis (Part B)	53
6.1 Treatment-Emergent Adverse Events	53
6.1.1 Overview of Treatment-Emergent Adverse Events	53
6.1.2 Displays of Treatment-Emergent Adverse Events	54
6.2 Pretreatment Events	56
6.2.1 Displays of Pretreatment Events	56
6.3 Laboratory and Other Safety Data	57
6.3.1 Laboratory Test Results	57
6.3.2 Vital Signs, Physical Findings, and Other Observations Related to Safety	60
6.4 Displays of Treatment-Emergent Adverse Events (Japanese)	62
7 Significance Level and Confidence Coefficient (Part A and Part B)	62
Amendment History	63
Appendix 1. Amendments from the Previous Version	1
Appendix 2. Criteria for Markedly Abnormal Values and Elevated Liver Enzyme	1
Appendix 3. QOL Scoring Procedures	1

Glossary

- Treatment-emergent adverse event (TEAE): An adverse event whose date of onset occurs on or after the start of study drug
- Descriptive statistics: number of subjects, mean, standard deviation (SD), maximum (max), minimum (min), and quartiles
- CV: coefficient of variation
- Randomized set: All subjects who were randomized. The first maintenance dose prescribed will be used as the treatment group when conducting analyses.
- Treatment group: For part A, the assigned cohort will be the treatment group. For part B, the first maintenance dose prescribed will be the treatment group.
- PK: pharmacokinetic
- MAV: markedly abnormal value
- ATC: anatomical therapeutic chemical
- LDH: lactic dehydrogenase
- GGT: gamma-glutamyl transpeptidase
- CK (CPK): creatine phosphokinase/kinase
- Study Day: The day before the first dose of the study drug will be defined as Study Day -1 and the day of the first dose will be defined as Study Day 1. If the date of the observation is on the same date or after the day of the first dose, Study Day will be calculated relative to Study Day 1. Otherwise, Study Day will be calculated relative to Study Day -1.
- Follow-up Day: The day after the last dose of the study drug will be defined as Follow-up Day
 1. Follow-up Day will be calculated relative to Day 1.

Definition of Visit Window

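### The last onset class in the Part A TEAE table joins one on-drug week to 30-40 off-drug days, which can inflate that column and hides Week 4 (minor)

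*SAP*

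**What the plan says.** SAP 5.1.2 sets the Part A time-of-onset classes, in days, at "1<=-<=7, 8<=-<=14, 15<=-<=21" plus an open class from Day 22 to the maximum. Summary (11) of that section gives a percentage per class. The denominator rule begins "When calculating percentages for each time interval, the number of subjects at risk" and defines those men as having either an exposure or a TEAE during or after the interval. The numerator is the men with an onset in the interval. Person-time is not used and nothing is scaled for interval length.

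The span of the open class follows from four other statements:

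- Protocol 6.1: "TAK-385 will be taken once a day for 28 days at the doses assigned to each cohort".
- SAP Glossary, definition of a TEAE: "An adverse event whose date of onset occurs on or after the start of study drug". No end date is set.
- Protocol 10.2.1.1: "AEs will be recorded continuously from the start of study drug administration to subjects (Day 1) until the safety follow-up".
- Protocol 9.3.8 places the visit as "safety follow-up 30 to 40 days after the day of the last dose of study drug". Appendix A of the Protocol gives the same collection period for Part A.

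Protocol 6.1 and Table 6.a also provide a no-treatment week after Day 28, after which another therapy may start before the safety follow-up.

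**The concern.** A reader of an onset table compares columns. Three of these columns describe a week on drug. The fourth describes a week on drug, a week without treatment, and several more weeks in which some men may already be on a GnRH agonist or another antagonist. A larger fourth column could mean that events appear late in dosing, or only that the column covers more days. The table cannot say which.

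Timing has some interest here. Protocol 4.1.2.5 reports that in the earlier healthy-volunteer study raised transaminases seemed more likely within 2 weeks at higher doses, and Protocol 10.1.5.1 makes liver function abnormalities the adverse event of special interest. Week 4 also belongs to the DLT evaluation period (Protocol 6.1.2.2), yet no TEAE table specified for Part A separates on-drug from off-drug onsets.

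**Working it through.** The documents state no figure for this table, so there is nothing to reproduce first.

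**Length of the last class, for a man who takes all 28 days.** With follow-up f = 30 or 40 days after the last dose, the last day of collection is 28 + f = Day 58 or Day 68.

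- Length = (28 + f) - 22 + 1 = 37 or 47 days.
- Ratio to a 7-day class: 37/7 = 5.3; 47/7 = 6.7.
- On drug: Days 22-28, 7 days. Off drug: 30/37 = 81% or 40/47 = 85%.

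**Expected percentage in the last class.** Let p be the incidence in a 7-day on-drug class, taken as the same in all four on-drug weeks, and r the off-drug daily rate divided by the on-drug daily rate. Then

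incidence = 1 - (1 - p)^((7 + r × f)/7).

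Neither p nor r is in the documents; both are assumptions, shown over a range. Each cell gives f = 30 to f = 40.

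| p | r = 0 | r = 0.1 | r = 0.25 | r = 0.5 | r = 1 |
|---|---|---|---|---|---|
| 5% | 5% | 7.1-7.7% | 10.1-11.7% | 14.9-18.0% | 23.7-29.1% |
| 10% | 10% | 14.0-15.3% | 19.6-22.6% | 28.2-33.4% | 42.7-50.7% |
| 20% | 20% | 27.3-29.6% | 37.0-41.8% | 50.4-57.7% | 69.3-77.6% |
| 30% | 30% | 39.9-42.9% | 52.2-57.9% | 67.4-74.7% | 84.8-90.9% |

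Example: p = 10%, r = 0.25, f = 30 gives 1 - 0.9^(14.5/7) = 19.6%.

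**When the column would not rise.** It does not rise if r = 0, or if the mean daily rate over the last class falls by at least 5.3- to 6.7-fold. If the on-drug rate in Week 4 is already half that of the earlier weeks, the last column exceeds them only when the off-drug rate is above (7 - 3.5)/40 = 0.09 to (7 - 3.5)/30 = 0.12 of the earlier rate.

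**Early stoppers.** A man whose last dose is Day 14 is followed to Day 44-54, so his last class is 23 to 33 days, all off drug. Under the at-risk rule, a man who stops before Day 22 enters the last denominator only if he has a TEAE on or after Day 22. That also pushes the percentage up.

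**Comparison within the SAP.** SAP 1.3.1 uses the same cut-points for duration of exposure, where the maximum is about Day 28 and the last class is a true fourth week. The Part A laboratory, vital-sign and ECG windows have their own follow-up window (Follow-up Day 15-40). In Part B (SAP 6.1.2) the last onset class for a 96-week completer runs from Day 631 to Day 672 + 30 or 40 = 702 or 712, which is 72 to 82 days against 90 in the earlier classes. The inflation is therefore specific to Part A.

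**A bare split is not enough.** Under the schedule nobody has exposure after Day 28. With the present at-risk rule, a class of Day 29 to maximum would count in its denominator only men with a TEAE in it. If one of six completers had such an onset, the any-TEAE row would read 1/1 = 100%, where 1/6 = 17% is meant.

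**The case against.** Protocol 13.1.7 asks only for a frequency tabulation of TEAEs by time of onset, and a TEAE has no upper time limit. A last class that runs to the maximum delivers that, and the SAP plans no test or trend across classes. Tolerability rests on DLTs in Days 1-28, which SAP 5.1.3 tabulates on the DLT analysis set; the advancement rules in Protocol 6.1.1 do not use the onset table. Cohorts have 3 to 6 men, so percentages move in steps of 1/6 to 1/3 (17 to 33 points) and most gradients would be unreadable anyway. Onset dates are recorded for every event, so Week 4 onsets can be recovered from the data.

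All of this stands and limits the importance of the point. It does not remove the ambiguity of the last column, because no rule in the SAP adjusts for length or marks post-treatment onsets.

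A reader might infer more: that the last column must rise, and by 3- to 6-fold. The documents do not support that. Such a rise needs an off-drug rate equal to the on-drug rate (r = 1 in the table above). No TEAE rate on or off drug is given, most of the class is off drug, and front-loaded onsets could cancel the effect. A reader might also infer that the Part A tolerability conclusion is affected. It is not, for the reasons above.

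**Conclusion.** The point holds as a minor defect of presentation. The unequal lengths (7, 7, 7 and 37-47 days for a completer) follow directly from the documents. The upward artefact is conditional: at a stable on-drug rate the expected last column equals or exceeds the others, with the excess set by an unknown off-drug rate. For p = 10% the range shown is no excess at r = 0 to 43-51% at r = 1. Apart from any inflation, the column cannot separate Week 4 on drug from post-treatment onsets, some of which may follow a switch of therapy. The calculation assumes completion of 28 days, a constant rate within each period, and follow-up on schedule.

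**What to change.** In SAP 5.1.2, for Time of Onset in Part A:

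1. Replace the open class from Day 22 with Days 22-28 and a separately labelled post-treatment class: Day 29 to maximum, or Days 29-35 and Day 36 to maximum.
2. State that any time trend is read only over the four 7-day classes.
3. For the post-treatment class or classes, use as denominator the men still under adverse-event observation, in place of the exposure-or-TEAE rule.
4. For men who stop early, assign onsets after the last dose to the post-treatment class, or flag them, so that Days 22-28 can be read as on drug.

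At a constant rate with p = 10%, the four weekly columns would then each have an expected 10%. The off-drug period would stand alone, at 1 - 0.9^(30/7) = 36% to 1 - 0.9^(40/7) = 45% if the rate did not change after dosing.

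The cost is SAP wording and one or two extra columns. No new data are needed and study conduct does not change.
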